### 5.1.2. Computerized Algorithm

A validated computerized algorithm (Attachment 2), which is based on the IMWG response criteria (Durie 2006, Rajkumar 2011) and has been used and validated by an independent review committee in study MMY2002, also used in MMY3003, MMY3004, MMY3007, and MMY3008 will be used to determine response and disease progression for each subject. Unless specified otherwise, relapse from CR by positive immunofixation or trace amount (defined as less than 0.5 g/dl) of M protein is not considered to be progressive disease in the IMWG response criteria.

The primary efficacy analyses will be based on the computerized algorithm assessments. Analyses for the primary endpoint ORR and selected major secondary efficacy endpoints based on investigator assessments using the IMWG response criteria will also be performed as sensitivity analyses.

### 5.1.3. Data Handling Rules

There is no imputation planned for missing efficacy endpoint values.

## 5.2. Primary Efficacy Endpoint(s)

### 5.2.1. Definition

The co-primary endpoint of this study for efficacy is overall response rate, which is defined as the proportion of subjects who achieve partial response (PR) or better according to the IMWG response criteria, including the subjects with either complete response (including stringent complete response [sCR]) or partial response (including VGPR), during or after treatment with study drug but at or prior to the start of subsequent anticancer therapy. Subjects with overall responses achieved after the start of subsequent anticancer therapy will not be considered as responders.

### 5.2.2. Estimand

The primary estimand, the main clinical quantity of interest to be estimated in the study, is defined by the following 4 components:

- Population: subjects with relapsed or refractory multiple myeloma who have received at least 3 prior lines of therapy including a PI and an IMiD, or whose disease is double refractory to both a PI and an IMiD;
- Variable: overall response, which is defined as response if the best response is PR or better assessed at or prior to the start of subsequent anticancer therapy and non-response otherwise;
- Intercurrent event: Treatment discontinuation is considered as an intercurrent event for overall response and treatment policy strategy will be implement, i.e., disease assessments ignoring the treatment discontinuation will be implemented.
- Population-level summary: relative risk of overall response between two treatment groups.

### 5.2.3. Analysis Methods

The primary analysis of ORR will be performed on the ITT analysis set. The number and percentage of subjects in the following response categories will be tabulated by treatment group: sCR, CR, VGPR, PR, minimal response (MR), stable disease (SD), progressive disease (PD), and not evaluable (NE). The overall response (including sCR + CR + VGPR + PR), VGPR or better (sCR + CR + VGPR), and CR or better (sCR + CR) will also be summarized. For each of the above categories, two-sided 95% Clopper-Pearson exact confidence interval (CI) will also be presented by treatment group.

Farrington-Manning (FM) test will be used to test the overall response rate. The FM estimate of relative risk with its 2-sided 95% confidence interval and p-value will be reported. If the lower bound of the 95% CI is  $\geq 60\%$ , the non-inferiority of Dara SC relative to Dara IV will be concluded. If non-inferiority in ORR is established and the lower limit of the 95% CI of the relative risk is  $\geq 100\%$ , the superiority of Dara SC relative to Dara IV will be concluded.

A sensitivity analysis of ORR based on the per-protocol and response-evaluable analysis sets will be performed in a similar manner as described above.

A sensitivity analysis of ORR, in which disease response is based on investigator assessment according to the IMWG response criteria, will also be performed in a similar manner.

A supplementary analysis of ORR based on the first 480 randomized subjects in intent-to-treat analysis set will also be performed in a similar manner.

### **5.3. Major Secondary Endpoints**

The major secondary efficacy endpoints include progression-free survival (PFS), response rate of VGPR or better, response rate of CR or better, time to next therapy (TNT), overall survival (OS), duration of response (DOR), and time to response (TTR).

#### **5.3.1. Progression-free Survival**

##### **5.3.1.1. Definition**

PFS is defined as the duration from the date of randomization to either progressive disease, according to the IMWG response criteria, or death due to any cause, whichever occurs first.

Subjects who start subsequent anticancer therapies for multiple myeloma without disease progression will be censored at the last disease assessment before the start of subsequent therapies. Subjects who withdrew consent from the study before disease progression will be censored at the last disease assessment before withdrawal of consent to study. Subjects who are lost to follow-up will be censored at the last disease assessment before the subjects were lost to follow-up. Subjects who have not progressed and are still alive at the clinical cut-off date for analysis will be censored at the last disease assessment. Subjects without any post-baseline disease assessment will be censored at randomization.

Determination of dates of PFS event and dates for censoring is summarized in Table 2 as follows.

**Table 2: PFS Event and Censoring Method**

Situation	Date of Progression or Censoring	Outcome
No postbaseline disease assessment	Randomization	Censored
Disease progression at or prior to start of subsequent anticancer therapy	Earliest date that indicates disease progression	PFS event
Death at or prior to start of subsequent anticancer therapy	Date of death	PFS event
Other, such as: Withdrawal of consent to study participation, Lost to follow-up Start of subsequent anticancer therapy prior to disease progression or death	Date of last disease assessment prior to withdrawal of consent to study participation, lost to follow-up, or start of subsequent anticancer therapy	Censored

### 5.3.1.2. Analysis Methods

Analysis of PFS will be performed on the ITT analysis set. The Kaplan-Meier method will be used to estimate the distribution of overall PFS for each treatment group. The median PFS with 95% CI will be provided. The Kaplan-Meier curve for PFS will also be plotted by treatment group.

The PFS distributions between the 2 treatment groups will be compared using the stratified log-rank test. The p-value from a stratified log-rank test will be reported. The treatment effect (hazard ratio) and its 2-sided 95% CI will be estimated using a stratified Cox regression model with treatment as the sole explanatory variable. Stratification factors used in the analyses include body weight at baseline ( $\leq 65$  kg, 66 kg to 85 kg,  $>85$  kg), number of prior lines of therapy ( $\leq 4$  prior lines versus  $>4$  prior lines), and type of myeloma (IgG versus non-IgG).

In addition, the number and percentage of subjects who had a PFS event or were censored will be reported. The reasons for progressive disease and censoring of PFS will also be summarized for ITT analysis set.

A sensitivity analysis of PFS, in which progressive disease is based on investigator assessment according to the IMWG response criteria, will be performed in a similar manner as described above.

### **5.3.2. Response Rate of VGPR or Better**

#### **5.3.2.1. Definition**

Response rate of VGPR or better is defined as the proportion of subjects with a response of VGPR or better (VGPR, CR or sCR) according to IMWG response criteria, during or after treatment with study drug but at or prior to the start of subsequent anticancer therapy.

#### **5.3.2.2. Analysis Methods**

The response rate of VGPR or better will be calculated for each treatment group on both ITT and response-evaluable analysis sets. The corresponding 95% Clopper-Pearson exact CI will be provided.

Stratified CMH test will be used to test the proportion of subjects who achieved a VGPR or better response. The CMH estimate of odds ratio and its 95% confidence interval and p-value will be reported. Stratification factors used in the analysis include body weight at baseline ( $\leq 65$  kg, 66 kg to 85 kg,  $>85$  kg), number of prior lines of therapy ( $\leq 4$  prior lines versus  $>4$  prior lines), and type of myeloma (IgG versus non-IgG).

A sensitivity analysis of response rate of VGPR or better, in which disease response is based on investigator assessment according to the IMWG response criteria, will be performed in a similar manner as described above.

### **5.3.3. Response Rate of CR or Better**

#### **5.3.3.1. Definition**

Response rate of CR or better is defined as the proportion of subjects with a response of a CR or better (CR or sCR) according to IMWG response criteria, during or after treatment with study drug but at or prior to the start of subsequent anticancer therapy.

#### **5.3.3.2. Analysis Methods**

The response rate of CR or better will be calculated for each treatment group on both ITT and response-evaluable analysis sets. The corresponding 95% Clopper-Pearson exact CI will be provided.

An analysis of response rate of CR or better, in which disease response is based on investigator assessment according to the IMWG response criteria, will be performed in a similar manner as described above.

### **5.3.4. Time to Next Therapy**

#### **5.3.4.1. Definition**

Time to next therapy is defined as the time from randomization to the start of subsequent anticancer therapy for multiple myeloma. Death due to PD without start of subsequent anticancer therapy will be considered as event. Subjects who withdrew consent to study or are lost to

follow, or die due to causes other than disease progression or subjects without receiving subsequent anticancer therapy will be censored at date of death or the last date known to be alive.

#### **5.3.4.2. Analysis Methods**

TNT will be analyzed using similar statistical methods as described in Section 5.3.1.2 for PFS analysis.

#### **5.3.5. Overall Survival**

##### **5.3.5.1. Definition**

Overall survival is defined as the time from the date of randomization to the date of the subject's death due to any cause. Death after end of study will also be considered as an OS event.

Subjects who are lost to follow-up will be censored at the time of lost to follow-up. Subject who is still alive at the clinical cut-off date for the analysis will be censored at the date of last known to be alive. The date of last known to be alive will be determined by the maximum collection/assessment date from among selected data domains within the clinical database.

##### **5.3.5.2. Analysis Methods**

OS will be analyzed using similar statistical methods as described in Section 5.3.1.2 for PFS analysis.

A summary of reasons for censoring of overall survival will be provided.

#### **5.3.6. Time to Response**

##### **5.3.6.1. Definition**

Time to response (i.e., time to first response) is defined as the time from the date of randomization to the date of initial documentation of a response of PR or better based on the computerized algorithm for patients who had PR or better as their best response.

##### **5.3.6.2. Analysis Methods**

For the subjects who achieve a response of PR or better, descriptive statistics (n, mean, standard deviation, median, and range) will be provided to summarize TTR for the responders in each treatment group.

The similar analyses will be conducted for time to response of VGPR or better and time to response of CR or better.

No formal statistical comparison of TTR between the treatment groups will be made.

### **5.3.7. Duration of Response**

#### **5.3.7.1. Definition**

Duration of response is calculated from the date of initial documentation of a response (PR or better) to the date of first documented evidence of progressive disease as defined according to IMWG criteria or death due to PD, whichever occurs first, for the subjects who had achieved a response of PR or better.

Subjects who start subsequent anticancer therapies without PD will be censored at the date of the last disease assessment prior to the start of subsequent anticancer therapies. Subjects who have not progressed or subjects who die due to causes other than disease progression will be censored at the last disease assessment date.

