2.1.2. Endpoints

Primary Endpoints

The co-primary endpoints of this study are:

- ORR, defined as the proportion of subjects with a PR or better according to the International Myeloma Working Group (IMWG) response criteria
- Maximum C_{trough} , defined as the serum predose concentration of daratumumab on Cycle 3 Day 1

Secondary Endpoints

- Rate of IRRs
- PFS, defined as the time from randomization to the date of disease progression or death due to any cause, whichever occurs first
- Rate of VGPR or better, according to the IMWG response criteria
- Rate of CR or better, according to the IMWG response criteria
- Time to next therapy (TNT), defined as the time from randomization to the start of the first subsequent anti-cancer therapy

- OS, defined as the time from randomization to the date of death
- Patient-reported satisfaction with therapy, defined as the mean of responses to 7 of 9 questions in the modified Cancer Therapy Satisfaction Questionnaire (modified-CTSQ)
- Duration of response, defined as date of onset of first response until date of disease progression or death
- Time to response, defined as the time from randomization until onset of first response

Refer to Section 9, Study Evaluations for evaluations related to endpoints.

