#### **5.3.7.2. Analysis Methods**

Analysis of DOR will be based on subjects who achieved a response of PR or better. Median DOR with 95% CI will be estimated based on the Kaplan-Meier method for each treatment group. The Kaplan-Meier curve for DOR will be plotted by treatment group.

No formal statistical comparison of DOR between the treatment groups will be made.

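### The SAP's duration-of-response event omits deaths not due to progression, contrary to the protocol, and PFS Table 2 gives a death before any post-baseline assessment two opposite outcomes

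*SAP*

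**What the plan says.** **DOR.** Protocol Section 2.1.2 reads: "Duration of response, defined as date of onset of first response until date of disease progression or death". No cause of death is specified. SAP Section 5.3.7.1 ends the response at progression "or death due to PD, whichever occurs first, for the subjects who had achieved a response of PR or better". Its censoring rule matches that narrower event: "subjects who die due to causes other than disease progression will be censored at the last disease assessment date". SAP Section 5.3.7.2 estimates the median with a 95% CI by Kaplan-Meier in each group and adds: "No formal statistical comparison of DOR between the treatment groups will be made". Protocol Section 11.4 also makes DOR descriptive.

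**PFS.** The SAP Section 5.3.1.1 definition counts progression "according to the IMWG response criteria, or death due to any cause, whichever occurs first", in agreement with Protocol Section 2.1.2. The censoring paragraph of the same section ends: "Subjects without any post-baseline disease assessment will be censored at randomization". The first row of Table 2 ("No postbaseline disease assessment") repeats this: date of randomisation, censored. A later row ("Death at or prior to start of subsequent anticancer therapy") gives the date of death and a PFS event. Neither row refers to the other.

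**The concern.** For DOR, the SAP does not add detail to the protocol's definition; it changes the event. A responder who dies of infection, for example, leaves the risk set as though progression could still occur later, and the Kaplan-Meier median lengthens. The SAP rule also makes the event depend on attribution of cause of death in an open-label trial, which the protocol's definition avoids.

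For PFS, a subject who dies before the first post-baseline assessment and before any new therapy satisfies two rows with opposite outcomes. PFS is the second of the four hierarchically tested secondary endpoints in SAP Section 5.1.1, so its event rule should have a single reading before the data are analysed.

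**Working it through.** Neither document states a figure for DOR or PFS, so there is none to reproduce. The planned sample size concerns ORR and does not depend on either rule. The check is therefore a comparison of the definitions, followed by illustrations of size.

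**Definitions side by side**

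| Subject | Protocol 2.1.2 | SAP |
|---|---|---|
| Responder, death not due to PD, no prior PD or new therapy: DOR | Event | Censored at last assessment (5.3.7.1) |
| Same responder: PFS | Event | Event at death (5.3.1.1, Table 2) |
| Death before any post-baseline assessment and before new therapy: PFS | Event | Censored at randomisation (Table 2 first row, 5.3.1.1 last sentence) and event at death (Table 2 death row, 5.3.1.1 definition) |

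The first two rows show that the SAP also treats the same death differently in DOR and PFS.

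**Size, DOR.** Let λ be the hazard of progression or PD death and μ the hazard of other death, both constant. The share of first events that are non-PD deaths is q = μ/(λ+μ). The SAP rule estimates a median of ln2/λ; the protocol's event gives ln2/(λ+μ). The ratio is 1/(1−q), so the overstatement is 1/(1−q) − 1:

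- q = 2%: 1/0.98 − 1 = 2.0%
- q = 5%: 1/0.95 − 1 = 5.3%
- q = 10%: 1/0.90 − 1 = 11.1%

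In months, suppose the SAP median is 12. If μ is 5%, 10%, 20% or 30% of λ, the protocol's median is 12/(1+μ/λ) = 11.4, 10.9, 10.0 or 9.2 months. The last two correspond to q = 17% and 23%, a deliberately wide range. At the ORR of 29.2% from Study MMY2002, responders per arm are 0.292 × 240 ≈ 70, so q of 5% to 10% is at most 4 to 7 subjects per arm (70 × 0.05 = 3.5; 70 × 0.10 = 7.0).

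**Size, PFS.** Disease evaluations are every 28 ± 7 days (Protocol Section 9.2.1), so the first falls on about day 21 to 35. Protocol Section 1.2.1.1 gives a median OS of 20.1 months on Dara-IV in MMY2002. With exponential survival, P(death by day d) = 1 − 2^(−(d/30.44)/20.1):

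- day 21: 2.35%, × 480 = 11.3 subjects
- day 28: 3.12%, × 480 = 15.0 subjects
- day 35: 3.89%, × 480 = 18.7 subjects

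This is an upper illustration. The ECOG and organ-function entry criteria lower early risk, and some of these subjects will have been assessed.

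Suppose a share p dies very early and unassessed, and PFS is exponential in the rest. Counting the deaths gives a survival curve of (1−p) times the exponential; censoring them at time zero leaves the exponential alone. The ratio of medians, censored over counted, is ln2/(ln2 + ln(1−p)):

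- p = 1% (about 5 of 480): 1.015
- p = 2% (about 10 of 480): 1.030
- p = 2.35%, 3.12%, 3.89%: 1.036, 1.048, 1.061

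**The case against.** Protocol Section 11 leaves specific details to the SAP. The SAP's DOR rule is explicit, has a matching censoring sentence, and can be programmed only one way. It looks deliberate, since time to next therapy uses a similar PD-death rule. DOR carries no test, the rule is the same in both arms, and at the primary analysis many responders may have had no event, so few non-PD deaths may be involved. On PFS, both documents define the event by death from any cause, and censoring rules ordinarily apply to subjects without an event. PFS2 Table 3 has the same first row, while its text says that every death is an event. The censoring row was probably never meant to override a death.

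Much of this stands as a limit on size. The magnitudes rest on assumed rates, no between-arm bias follows, and death was probably meant to prevail in PFS. It does not remove either point. Leaving details to the SAP does not extend to replacing the event that defines a protocol endpoint, and a clear SAP rule that contradicts the protocol is still a contradiction. For PFS, the clarifying sentence in the PFS2 section is missing from the PFS section, so a programmer can follow either row.

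**Conclusion.** Both points hold on the current text. The DOR rule contradicts the protocol and generally lengthens the reported median, by about 5% to 11% if non-PD deaths are 5% to 10% of first events. That range assumes constant hazards and a share the documents do not provide. The PFS table is ambiguous for deaths before any post-baseline assessment. If the censoring row were applied, the median would be overstated by about 1.5% to 3% for 1% to 2% unassessed early deaths, and by 3.5% to 6% at the upper illustration. The textual differences are certain; the sizes are illustrative. The ORR and maximum trough analyses and the sample size are unaffected. These points should be corrected, but they do not threaten the primary conclusion.

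**What to change.** 1. **SAP Section 5.3.7.1:** define the DOR event as the first of progression or death from any cause, as in Protocol Section 2.1.2, and delete the censoring of non-PD deaths. The PD-death version can be kept as a labelled sensitivity analysis.
2. **SAP Section 5.3.1.1, last sentence of the censoring paragraph, and Table 2, first row:** restrict censoring at randomisation to subjects with neither a post-baseline disease assessment nor a death.
3. **Housekeeping:** the definitions of time to next therapy also differ. SAP Section 5.3.4.1 adds PD deaths as events and Protocol Section 2.1.2 does not. Make them agree; neither is shown to be wrong.

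The cost is SAP wording and derivation code, with no new data. Median DOR may come out slightly shorter.

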#### **5.3.7.2. Analysis Methods**

Analysis of DOR will be based on subjects who achieved a response of PR or better. Median DOR with 95% CI will be estimated based on the Kaplan-Meier method for each treatment group. The Kaplan-Meier curve for DOR will be plotted by treatment group.

No formal statistical comparison of DOR between the treatment groups will be made.

### **5.4. Other Efficacy Endpoints/Variables**

Other efficacy endpoints include the proportion of subjects with best M-protein response for subjects with measurable disease in serum or urine, and the proportion of subjects with maximal reduction of  $\geq 90\%$  and  $\geq 50\%$  from baseline in the difference between involved and uninvolved serum FLC (dFLC) for subjects with measurable disease of FLC only, and exploratory efficacy endpoint of progression-free survival on next line of therapy (PFS2).

#### **5.4.1. Best M-protein/dFLC Response**

##### **5.4.1.1. Definition**

Serum/urine M-protein or FLC reduction, defined as the percent change from baseline at each post-baseline assessment visit in the quantitation of the corresponding serum/urine M-protein or FLC, according to the measurable type at baseline.

Best M-protein response is defined as the maximal percent reduction or the lowest percent increase from baseline in serum M-protein for subjects with measurable heavy chain at baseline or urine M-protein for subjects without measurable heavy chain, but with measurable light chain disease at baseline.

For subjects without measurable heavy chain and light chain disease at baseline, best response in serum dFLC is defined as the maximal percent reduction or the lowest percent increase from baseline in the difference between involved and uninvolved serum FLC level.

#### 5.4.1.2. Analysis Methods

The number and percentage of subjects in each response category, along with presentation of  $\geq 90\%$  reduction and  $\geq 50\%$  reduction, will be tabulated for each treatment group.

#### 5.4.2. Progression-free Survival on Next Line of Therapy (PFS2)

##### 5.4.2.1. Definition

Progression-free survival on next line of therapy (PFS2) is defined as the time from randomization to progression on next line of therapy or death, whichever comes first. Any deaths are considered as PFS2 events, including the deaths after end of study.

Subjects who start next line of therapy without disease progression on study treatment will be censored at the last disease assessment before starting next line of therapy. For subjects who start next line of therapy after progression on study treatment, are still alive and not yet progress on next line of therapy, they will be censored on the last date of follow-up. Subjects without any post-baseline follow-up will be censored at the randomization.

Determination of dates of PFS2 event and dates for censoring is summarized in Table 3 as follows.

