#### **2.9.9. End of Follow-up and Duration of Follow-up**

The end of follow-up is defined as the maximum date of the following study evaluations: labs (hematology, chemistry, immunology), adverse events, vital signs, ECOG performance status, PRO assessment, bone marrow cytogenetics, lytic bone lesions, extra-medullary plasmacytomas, study drug administration, ECG, pre-dose medications, post-dose medications, concomitant medications, subsequent therapy, medical encounters, clinical events/disease response per investigator and date of last known to be alive. For subjects who died on study, the end of follow-up is the date of death. For subjects who died after the end of study, the end of follow-up will be set to the maximum date derived above.

Duration of follow-up (in months) = the date of end of follow-up - the date of randomization + 1, divided by 365.25/12.

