**Table 3: PFS2 Event and Censoring Method**

Situation	Date of Progression or Censoring	Outcome
No postbaseline disease assessment	Randomization	Censored
Alive and no disease progression on study treatment	Date of last disease assessment prior to start of 1st line on next therapy	Censored
Disease progression on study treatment and progress on the 1 st line of next therapy or any death	Minimum of earliest date that indicates progression on the 1 st line of next therapy and date of death	PFS2 event
Other	Minimum of start date of 2 nd line of next therapy minus 1 and last date of follow-up	Censored

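### PFS2: the SAP text and Table 3 give conflicting rules for deaths, and the definition disagrees with the censoring of living subjects who switch therapy without progression

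*SAP*

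**What the plan says.** SAP 5.4.2.1 states that PFS2 "is defined as the time from randomization to progression on next line of therapy or death, whichever comes first". It adds: "Any deaths are considered as PFS2 events, including the deaths after end of study". Three censoring sentences follow:

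- Switchers without progression: "Subjects who start next line of therapy without disease progression on study treatment will be censored at the last disease assessment" before the next line starts.
- Subjects who progressed on study treatment, started the next line, and are alive without progressing on it are censored at last follow-up.
- "Subjects without any post-baseline follow-up will be censored at the randomization".

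Table 3 then gives four rows:

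1. "No postbaseline disease assessment": censored at randomization.
2. "Alive and no disease progression on study treatment": censored at the last disease assessment before the first next line.
3. Progression on study treatment and then on the first line "of next therapy or any death": an event, dated at the earlier of next-line progression and death.
4. Other: censored at the earlier of last follow-up and the day before the second next line starts.

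SAP 2.9.9 defines follow-up through many data sources besides disease assessment, and says: "For subjects who died on study, the end of follow-up is the date of death".

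SAP 5.4 calls PFS2 exploratory. SAP 5.4.2.2 analyses it by investigator assessment in the ITT set with the PFS methods, which include a stratified log-rank test and a Cox hazard ratio. It is not in the testing order of SAP 5.1.1.

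**The concern.** An event rule has to give one outcome and one date for each subject history. Here some histories get two. A subject who dies before any disease assessment matches both an event row and a censoring row of the same table. A subject who switches without progression and then dies is an event by one sentence of the text and censored by another. Nothing says which rule prevails, so two programmers could follow the SAP and report different event counts.

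There is a second, separate mismatch. The definition does not ask for progression on study treatment before progression on the next line counts. The censoring rules do ask for it while the subject is alive. A reader of the definition would expect events that the analysis does not contain.

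The stake is limited to the reproducibility and meaning of an exploratory endpoint. Its arms are still to be compared by hazard ratio, and SAP Attachment 1 also analyses it by subgroup.

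**Working it through.** The documents give no event count or power for PFS2, so there is no figure to reproduce. The check is to run subject histories through the three sets of rules.

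| History | Definition | Text of 5.4.2.1 | Table 3 |
|---|---|---|---|
| A. No post-baseline disease assessment, no next line, died on study | Event | Event | Row 1 censors at randomization; row 3 event |
| B. Switched without progression, died without next-line progression | Event | Death sentence: event; switcher sentence: censored | Row 3 event (row 2 needs the subject alive) |
| C. Switched without progression, progressed on next line, alive | Event | Censored before the switch | Row 2 censors before the switch |
| D. As C, then died | Event | Event and censored, as in B | Row 3 event, dated at next-line progression |
| E. Progressed on study, then progressed on next line or died | Event | Event | Row 3 event |
| F. Progressed on study, alive, no progression on next line, started a second next line | No event | Censored at last follow-up | Last row: day before second next line, if earlier |
| G. No disease assessment but other follow-up, alive, no next line | No event | Not censored at randomization | Row 1 censors at randomization |

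What follows:

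- **A** is a contradiction inside Table 3. The text does not share it: an on-study death date is follow-up under SAP 2.9.9, so the text's trigger for censoring at randomization is not met.
- **B** is a contradiction inside the text. Table 3 resolves it in favour of an event.
- **C** is a mismatch between the definition and the rules. Text and table agree with each other.
- **C against D**: the same next-line progression is ignored while the subject lives and becomes the event date if the subject later dies.
- **F and G** lose no event, but the censoring date depends on which rule is read.

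**Scale, as an illustration only.** From the documents: median OS 20.1 months (MMY2002, Protocol 1.2.1.1) and 24 months of follow-up (Protocol 3.1). Assumed: independent exponential times, median 4 months to leaving study treatment and 4 more months to next-line progression; a share s switching without progression.

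- Alive at 24 months: 2^(−24/20.1) = 0.437.
- Next-line progression time reached by 24 months: 1 − 2^(−24/4) × (1 + 24 × ln 2 / 4) = 1 − 0.0156 × 5.159 = 0.919.
- Any defined event by 24 months: 1 − 0.437 × 0.081 = 0.965.
- Share of defined events that are history C: s × 0.437 × 0.919 / 0.965 = 0.416 s, that is 2.1%, 4.2%, 8.3% and 12.5% for s = 5%, 10%, 20% and 30%.

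The widest reading lets the switcher sentence and row 1 override the rule on deaths. With a share q of subjects lacking any assessment:

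- Switch before death and before 24 months: (1/4) / (1/4 + 1/20.1) × (1 − 0.0156 × 0.437) = 0.828.
- Less those with no event by 24 months: (0.081 − 0.016) × 0.437 = 0.028, leaving 0.800; as a share of events, 0.800 / 0.965 = 0.829.
- Events censored: 1 − (1 − 0.829 s)(1 − q). For q = 2% to 5% this is about 6–9%, 10–13%, 18–21% and 26–29% at the same four values of s.

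The gap between the two sets of figures shows how far the choice of precedence could move the event count. None of the rates or times marked as assumed is in the documents.

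**The case against.** The strongest reply is that the SAP's intention on deaths is clear. The sentence on deaths has no exception and comes before the censoring sentences. Row 2 is confined to living subjects, row 3 counts any death, and the text points to the table for event and censoring dates. On that reading a subject who switches and then dies is an event. This largely stands for history B. It does not settle history A, where the conflict lies within the table itself.

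The reply on living switchers is also fair. Censoring them matches the SAP's PFS rule (5.3.1.1), text and table agree, and two programmers would not differ. Whether their next-line progression should count is a choice of estimand. What remains is that the stated definition does not describe that choice.

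Four stronger readings are tempting, and the documents do not support them:

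- **That the plan plainly discards deaths.** It does not: two rules keep them, and the defect is conflict without precedence. A living subject with no assessment and no next line has no event to lose.
- **That a substantial share of subjects is affected.** No switching rate is given. The nearest figure, 6 of 156 subjects (4%) stopping Dara-IV monotherapy for an adverse event (Protocol 1.2.1.1), is not a switching rate.
- **That the censoring biases the comparison through differing tolerability.** This is possible, but nothing in the documents shows that switching without progression would differ between arms.
- **That all the data for a fuller rule are in hand.** Subsequent therapy and survival are collected throughout (Protocol Table 1). Response to later therapy and date of progression are described only after progression is documented (Protocol 9.1.4 and Table 1 footnote a), and scheduled disease evaluations stop when a new myeloma treatment starts (Protocol 9.2.1).

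**Conclusion.** The point holds as a specification defect. On deaths, Table 3 row 1 conflicts with row 3 and with the text, and the switcher sentence lacks the limit to living subjects that row 2 carries. The trigger for censoring at randomization and the censoring date in the last row also differ between text and table. Separately, the definition is wider than the rules for living subjects who switch without progression.

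The consequence is small. PFS2 is exploratory, carries no alpha and supports no stated decision. The effect on the event count cannot be estimated from the documents; the percentages above depend on assumed switching rates and event times. The conflict on deaths is a clear correction. The treatment of living switchers is a choice that only needs to be stated consistently.

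**What to change.** Amend SAP 5.4.2.1 and Table 3 together:

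1. State that death from any cause is an event and overrides rows 1 and 2 and the switcher sentence.
2. Limit censoring at randomization to living subjects with no post-baseline follow-up, with the same trigger in text and table.
3. Give one censoring date for subjects who progressed on study treatment and are alive without next-line progression, and say whether the start of a second next line ends follow-up.
4. Make the definition and the switcher rule agree. Either restate the definition to require progression on study treatment first, or count next-line progression regardless of it. Take the second option only after confirming that next-line progression is recorded for these subjects.
5. State the event date for a subject who switched without progression, progressed on the next line and later died, so that it follows from the option chosen in item 4.

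Items 1 to 3, item 5 and the first option in item 4 are SAP wording and cost almost nothing. The second option may also need a check of the case report form and, if the data are not there, a change in collection.
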